10.1.9 DATA HANDLING AND RECORD KEEPING

10.1.9.1 DATA COLLECTION AND MANAGEMENT RESPONSIBILITIES

Data management for this study will be overseen by the Infectious Diseases Research Collaboration (IDRC) Data Management Center located in the main IDRC research complex in Nakasero, Kampala, Uganda. The Data Management Center (DMC) is also responsible for providing IT support to all staff members.

Data Management System

For any study components using paper data collection, IDRC has designed and developed a custom Data Management System that is used to manage the data, using Microsoft SQL Server as the backend for all data storage. MS Access is used for double data entry and SAS programs are used for comparing 1st and 2nd entry and generating discrepancy reports. In addition, the DMC has developed custom Visual Basic programming for direct survey and data entry of data in the field. Data Transformation Services/ SQL Server Integration Services (DTS/SSIS) packages are used to automatically import/export any new data and stored procedures written in T-SQL are used to automatically generate new data queries on a daily basis. There is a web interface to the whole system written in ASP.NET to allow users to view the data,

view reports, and even modify the data they are authorized to access. With regular backups and a full audit trail, the whole system is regulatory compliant (21 CFR Part 11).

Data Quality Assurance Process

The data management system is designed to collect, transfer and store data for Data Management Center studies. Data from any paper records will be 100% double entered into the system via Microsoft Access Databases or Web-based data entry screens. Locally collected data is compressed, password-protected, and then securely uploaded to a cloud based server (Network Solutions, Inc) using secure-FTP via the FileZilla application. Cloud-based uploads are downloaded daily to the Kampala DMC. After the data has been input into the Data Management Center server, it is electronically verified and is then written to the SQL database. Edit checks or queries are run nightly and the results are posted to a secure clinical trials website so that the sites can electronically address problems with the data the next day. The site corrects data via the website and the database is updated automatically.

In order to ensure data security and integrity, the following measures will be implemented:

- All members of the study team will be educated in the study protocol prior to the onset of the study.
- Detailed Standard Operating Procedures (SOPs) will be written for all project activities and be provided to relevant team members.
- Team members will be thoroughly trained on the SOP's.
- Where applicable, team members will receive additional training on the use of tablet computers.
- All data transcribed from paper will be double data entered or verified.
- All electronic data will be backed up regularly.
- All data will be transferred to the main Data Center in Kampala to the secure server. This sever is backed up on a daily basis and a monthly backup is stored off-site.
- All computers, including the tablets, will be password protected.
- All computers, including tablets, will be locked in a secure room each night.
- Any Log Books and CRF's will be locked in a secure room each night.

10.1.9.2 STUDY RECORDS RETENTION

Data archives will be kept for periods based upon the terms of the agreement between the funding organization and IDRC. Datasets that are required to be retained for periods as prescribed by law will also be kept following the respective durations as set in the enacted laws of Uganda. In general, study data will be kept electronically for a period of at least 5 years post completing of the study. Data will remain on the password secured IDRC servers and on the system of annual USB physical backup drives. After 5 years from the close of the study, all paper records will be destroyed and the electronic records will be removed from the server, but retained on Archival, password-protected USB drives.

10.1.10 PROTOCOL DEVIATIONS

It will be the responsibility of the site investigators and staff to use continuous vigilance to identify deviations or violations and report violations that meet the IRB definition of reportable events. Protocol violations that occur at UCSF will be reported to the UCSF CHR IRB within 10 working days of the PI's awareness. Protocol violations that occur on-site will be reported to the SOMREC IRB within 7 working days. SOPs will describe the process for communicating with study coordinators and investigators and the event reporting procedures.

10.1.11 PUBLICATION AND DATA SHARING POLICY

The findings from this study may be published in a medical journal. No individual identities will be used in any reports or publications resulting from the study. The researchers will publish results of the study in accordance with NICHD, UCSF, UNCST, KEMRI and Makerere University guidelines.

10.1.12 CONFLICT OF INTEREST POLICY

Any actual conflict of interest of persons who have a role in the design, conduct, analysis, publication, or any aspect of this trial will be disclosed and managed. Furthermore, persons who have a perceived conflict of interest will be required to have such conflicts managed in a way that is appropriate to their participation in the design and conduct of this trial. The study leadership in conjunction with the NICHD has established policies and procedures for all study group members to disclose all conflicts of interest and will establish a mechanism for the management of all reported dualities of interest.

10.2 ADDITIONAL CONSIDERATIONS

N/A.

10.3 ABBREVIATIONS AND SPECIAL TERMS

ART	Antiretroviral Treatment
AYAH	Adolescents and Young Adults with HIV
CE	Cost Effectiveness
CFR	Code of Federal Regulations
CHR	Committee on Human Research (UCSF)
CMP	Clinical Monitoring Plan
CRF	Case Report Form
DALY	Disability-Adjusted Life Year(s)
DMC	Data Management Center

eCRF	Electronic Case Report Forms
GCP	Good Clinical Practice
HIV	Human Immunodeficiency Virus
ICF	Informed Consent Form
ICH	International Council on Harmonisation
IDRC	Infectious Diseases Research Collaboration (Uganda)
IRB	Institutional Review Board
KEMRI	Kenya Medical Research Institute
LTFU	Lost to Follow-Up
NASCOP	National AIDS and STI Control Programme
NCT	National Clinical Trial
NICHD	National Institute of Child Health and Human Development (NIH)
NIH	National Institutes of Health
NIH IC	NIH Institute or Center
OHRP	Office for Human Research Protections
PEth	Phosphatidylethanol
PI	Principal Investigator
PrEP	Pre-Exposure Prophylaxis
Q	Every
QA	Quality Assurance
QC	Quality Control
QMP	Quality Management Plan
RCT	Randomized Controlled Trial
SAE	Serious Adverse Event
SOA	Schedule of Activities
SOM-REC	School of Medicine Research and Ethics Committee (Makerere University)
SOP	Standard Operating Procedure
SSA	Sub-Saharan Africa
T&M	Time and Motion
UNCST	Uganda National Council on Science and Technology
UCSF	University of California, San Francisco
UP	Unanticipated Problem
US	United States
VL	HIV Viral Load

APPENDIX 1: RANDOMIZATION PRINCIPALS AND PROCEDURES

The location of the facility where the randomization event takes place should be a central venue that has been agreed upon by the local health leaders. The randomization strategy must be both scientifically valid and transparent to the community stakeholders and uses local idioms to make the concept of randomization easily understood by traditional leaders and community members. The random assignment within matched pairs of each site's communities to intervention or control status could employ a public lottery of community names to achieve maximum public acceptance of the randomization results by enhancing transparency and spreading ownership of the process. A computer randomly designates the randomization status for each pair of study communities only as the community name that would be 'picked up' or 'not picked up' in the public lottery. The lottery may be a public event with members of the CAB and local leadership present along with guests from other organizations with relationship to the health community.

The lottery could be conducted in a series of draws, one for each of the matched pairs of communities by their local leaders. For each drawing, the two clinic names are written on a separate piece of paper or card and folded in half to obscure the name from view. For the draw, the names of each matched pair could be placed in a sealed box with a hand hole cut out of the top of the box. A flip of a coin could be used to decide which of the two community leaders will pick the community name from the box. The unselected leader could be responsible for holding and shaking the selection box. The leader then draws a paper from the box without looking into the box and the picked-up community name was read aloud by both of the community leaders in turn. If the randomization protocol indicated that the "picked-up" community was to receive the intervention (i.e., the SEARCH Youth intervention components described in the protocol implemented for enrolled participants), then the host country Principal Investigator would announce the drawn clinic as an intervention clinic. If the protocol called for the "picked-up" clinic to be the control (i.e., community health campaigns and standard ART initiation), then the host-country PI would announce it as a comparison clinic. This process would assure equal chance of being randomized to the intervention or comparison arm, and eliminates any residual fears of bias or rigging.

APPENDIX 2: COSTING PRINCIPALS AND PROCEDURES

The costing team uses the standardized micro-costing workbook as the data collection tool to quantify the resources and associated unit costs to deliver the SEARCH Youth intervention components. These costs mainly consist of direct costs but also include some indirect costs such as infrastructure, administration, etc. Cost information will be gathered through examination of expenditure records, discussion with program staff and providers, care delivery logs, and other program documents. Each resource item used to deliver the SEARCH Youth intervention components will be enumerated under standard expenditure categories – personnel, recurrent goods (supplies), capital goods and equipment, services, and facility. The number of units consumed and unit cost of each resource item during the specified costing period will also be entered into the micro-costing workbook. The costing approach emphasizes resources used for service delivery and will include the value of all resources used even if not paid for by the SEARCH Youth study. The costing team will assign the full value to donated or subsidized resource items based on market price or existing data from similar costing analysis. The information sources (e.g., key informants and program documents) and the dates when the cost data were obtained are clearly documented in the micro-costing workbook. The costing team will also save relevant program documents and email communications for quality check and future references. The details of the costing process is outlined in a detailed SOP, which is used for training of staff and standardizing the process across all regions and clinics.

Costs Analysis

We will assess costs at least twice in each health facility: once before and once after adoption of the SEARCH Youth intervention, in order to estimate incremental costs of SEARCH Youth implementation and to compare costs of the intervention to standard of care. “Economic” costs (the true value of resources consumed or “opportunity cost”) will be assessed by identifying the value of subsidized or donated resources with information from data bases (e.g. wage rates) and donors, and, as needed, three price quotes from appropriate market sources.

Health Effects

To quantify health effects, we will use directly measured health-related study outcomes (e.g. viral suppression). Second, we plan to integrate the health impact of achieving viral suppression using disability-adjusted life years (DALYs), including years of life gained and the collective disability effects of living with HIV. We might be estimated as DALYs gained for the short term (during the trial) and the long-term (5, 10, and 20 years) using data from the trial, as well as morbidity and mortality attributed to un- or partially- treated HIV disease.

Sustainable East Africa Research in Community Health
(SEARCH) Collaboration

STRATEGIC ANTIRETROVIRAL THERAPY AND HIV TESTING
FOR YOUTH IN RURAL AFRICA (SEARCH-Youth)

**Statistical Analysis Plan for Primary and Selected
Secondary Health Endpoints of the SEARCH-Youth Study**

[name], PhD¹
[name], MD²
[name], MD²
for the SEARCH-Youth Study Team

April 14, 2022
Version 1.0

NCT03848728

¹School of Public Health & Health Sciences, University of Massachusetts Amherst, Amherst, USA
²Division of HIV, ID, & Global Medicine, Department of Medicine, UCSF, San Francisco, USA

Contents

1	Brief study overview	3
1.1	Study design	3
1.2	Description of population and context	3
2	Primary endpoint: Virologic suppression at 2 years	4
2.1	Sensitivity analyses	6
2.2	Subgroups	7
2.3	Participant flow and endpoint ascertainment	7
2.4	Predictor analyses	7
3	Impact of the roll-out of dolutegravir	8
3.1	Other potential mediators	9
4	Secondary health endpoints	9
4.1	Mortality	9
4.2	Documented transfers	10
4.3	Care engagement	10
4.4	Severe adverse events	10
5	Patient satisfaction surveys	11
6	Intervention implementation	11
7	Appendix	12
7.1	History of changes	12
7.2	Power calculations	12

1 Brief study overview

SEARCH-Youth is a cluster randomized trial designed to evaluate the effect of a combination intervention on HIV viral suppression among adolescents and young adults with HIV in rural Uganda and Kenya (Clinicaltrials.gov: NCT03848728). The patient-centered intervention was developed using the PRECEDE model of behavioral change and was designed to address the structural barriers and unique needs of the target population. Details of the trial design and procedures can be found in the Study Protocol. This document provides the statistical analysis plan to evaluate the intervention effect on the primary endpoint of viral suppression and selected secondary endpoints, including mortality, care engagement, and patient satisfaction. Analysis plans for qualitative outcomes, cost-effectiveness, and sub-studies are available elsewhere. A history of changes to this analysis plan is given in the Appendix.

1.1 Study design

SEARCH-Youth is an implementation science study, designed to rigorously evaluate the effects of a combination intervention, including life-stage assessments, structured choice clinic access, and rapid viral load feedback, on care outcomes among adolescents and young adults (15-24 years) with HIV. Since the personalized intervention is delivered through changes in clinical practice, the unit of randomization is government sponsored health clinics in rural western Kenya and southwestern Uganda. Specifically, a total of 28 clinics (14 per country) were randomized to the SEARCH-Youth intervention or the optimized standard of care: differentiated ART care, standard clinic hours, routine viral load monitoring, and access to 2nd and 3rd line ART. To improve statistical power, randomization occurred within strata defined by country, clinic size, and prior participation in the SEARCH Study (ClinicalTrials.gov: NCT01864603). Formal power calculations are given in the Appendix.

1.2 Description of population and context

We will provide a CONSORT diagram to detail participant flow from recruitment through inclusion in the primary analysis. We will also describe the study population with summary measures of baseline participant characteristics, including

- Age
- Sex
- Country
- Education
- Employment status
- Marital status
- Number of children
- Alcohol consumption

- Mobility
- ART regimen at enrollment
- HIV viral suppression, defined as HIV RNA <400 cps/mL
- Care status at enrollment
 - **Recently engaged:** started ART within the prior 6 months or at enrollment
 - **Engaged:** started ART more than 6 months ago, with a clinic visit in the prior 6 months
 - **Re-engaging:** started ART more than 6 months ago, without a clinic visit in the prior 6 months

We will provide these summary measures overall, by arm, by country (Kenya and Uganda), and within country by arm. We will also provide these summary measures at the clinic-level. We will additionally provide descriptions of secular events, non-study activities that could impact study outcomes, and measurement coverage of key endpoints.

2 Primary endpoint: Virologic suppression at 2 years

The primary endpoint is HIV viral suppression (HIV RNA <400 cps/mL) at 2 years of follow-up. Ideally, a HIV RNA measure (hereafter called “viral load”) would be obtained on every participant on the exact date marking 2 years of follow-up (hereafter called the “2-year mark”). However, such an approach is logically impossible and not responsive to study context, specifically the increased mobility expected given the participant’s life-stage and the ongoing COVID-19 pandemic. Therefore, for each participant, the endpoint window will begin 90 days prior to their 2-year mark and end at the nearest of 180 days after their 2-year mark or the date of database closure (March 1, 2022 for the primary endpoint).

Through rigorous study procedures, including clinic visits and home-based tracking, we will attempt to obtain a viral load on all participants during their endpoint window, regardless of their care status. (The exception will be persons who have formally been withdrawn from the study.) During endpoint ascertainment, we will also obtain each participant’s vital status and current residency. We will determine whether each participant lives within the study region, defined as < 3 hours traveling distance within the study country, or has **outmigrated**, defined as moving outside the study region. We will also review clinical records for documentation of formal transfers of care.

Inclusion/exclusion criteria: All analyses will exclude persons who have been withdrawn from the study. In the primary analysis, we will also exclude participants who have outmigrated or have formally transferred care. The excluded individuals do not represent the trial’s **target population**: adolescents and young adults with HIV who are living in the catchment area of the study clinics and, thus, able to benefit from the study intervention. Additionally, viral loads obtained on participants who outmigrated are likely to be enriched for persons engaged in care (e.g., they returned to the study clinic during the endpoint window or they transferred care and had a routine viral load available at their new clinic). As described below, secondary analyses will include participants who outmigrated as well as those who transferred. The primary analysis will also restrict to participants

enrolled prior to December 1, 2019; secondary analyses will include all participants, pending data availability.

Endpoint classification: We will classify participants as virally suppressed if their endpoint HIV RNA is < 400 cps/mL. In the primary analysis, we will classify participants as **failures** if they are unsuppressed (HIV RNA ≥ 400 cps/mL), if they have died prior to their endpoint viral load, or if the study was unable to obtain a viral load in their endpoint window. The reasons for incomplete viral load capture include participant's declining measurement, participant's not being found during tracking and without a routine viral load available, or that the sample was obtained after database closure.

Clinic-level endpoint: In the primary analysis, the endpoint (viral suppression or failure) is not subject to missingness. Therefore, in each clinic separately, we will calculate the proportion of participants meeting the inclusion criteria who are suppressing viral replication. In secondary analyses, we will also include participants who outmigrated and participants who formally transferred care. In sensitivity analyses, we will (i) exclude participants without an endpoint viral load measured, (ii) adjust for missingness (detailed below), (iii) treat transfers as successes, and (iv) censor at death.

In analyses subject to missingness or censoring, we will implement targeted minimum loss-based estimation (TMLE) in each clinic separately [1, 2]. TMLE allows flexible adjustment for the ways in which participants with measured endpoint viral loads could differ from participants without endpoint viral loads. Our adjustment set will consist of age, sex, and baseline viral suppression status. Our adjustment set will also include a post-baseline indicator of outmigration. To minimize the risk of model misspecification bias, we will use Super Learner, an ensemble machine learning method, to combine predictions from generalized linear models, generalized additive models, and the mean [3].

For each method, we will use influence curve-based inference to obtain 95% confidence intervals on the point estimate of the clinic-specific proportion with viral suppression.

Effect estimation: Viral suppression at two-years will be compared between randomized arms using *Two-Stage TMLE*, an approach that appropriately accounts for the dependence of outcomes within clusters [2]. In the first stage, viral suppression will be estimated for each clinic, as described above. In the second stage, we will use a cluster-level TMLE to evaluate intervention effectiveness by comparing the clinic-specific endpoints between randomized arms, adaptively selecting the clinic-level adjustment variables that optimize precision, while tightly preserving Type-I error control [2, 4, 5]. Specifically, we will use leave-one-out cross-validation to select from the following baseline covariates the combination that maximizes empirical efficiency: the clinic-specific number of adolescents and young adults in HIV care at baseline, the clinic-specific proportion with viral suppression among those engaged at baseline, or nothing (unadjusted). In secondary analyses, we will implement an unadjusted effect estimator as the contrast in the average proportion with viral suppression between arms.

The primary effect will be on the relative scale for the N=28 clinics in the trial (i.e., the sample

risk ratio) [6-10]:

$$\frac{\psi(1)}{\psi(0)} = \frac{1/N \sum_{i=1}^N \alpha_i Y_i(1)}{1/N \sum_{i=1}^N \alpha_i Y_i(0)}$$

where α_i are weights for the clinic i ; $Y_i(1)$ is the counterfactual proportion with viral suppression at 2 years if possibly contrary-to-fact clinic i were in the intervention arm ($Z = 1$), and $Y_i(0)$ is the counterfactual proportion with viral suppression at 2 years if possibly contrary-to-fact clinic i were in the standard-of-care arm ($Z = 0$). In secondary analyses, we will examine the effect on the absolute scale: $\psi(1) - \psi(0)$. Primary analyses will weight the N clinics equally: $\alpha_i = 1$ for all i . In sensitivity analyses (described below), we will weight according to the number of participants included in the analysis [5].

Statistical inference: In all analyses, we will use the influence curve for standard error estimation [2, 10]. All analyses will use the Student's t -distribution with $28-2=26$ degrees of freedom as finite sample approximation to the standard normal distribution [11].

We will test the *null hypothesis* that the SEARCH-Youth intervention did not improve viral suppression, as compared to the optimized standard-of-care, with a one-sided test at the 5% significance level. We will report point estimates and two-sided 95% confidence intervals for the arm-specific endpoints as well as the relative and absolute effects.

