2.1 Sensitivity analyses

In addition to the previously described sensitivity analyses, we will evaluate the intervention effect using a *Single-Stage TMLE* that pools across clinics to estimate and compare the average of individual-level outcomes between arms [2, 5, 12]. This approach naturally estimates an individual-level effect (e.g., the by-arm contrast in the overall proportion with viral suppression) and thus weights participants, not clinics, equally. As detailed in [5], however, this effect can equivalently be estimated with Two-Stage TMLE when the appropriate weights are applied. The single-stage approach is preferable when the cluster size is small or the outcome is rare. (The two-stage approach is preferable when the outcome is subject to differential measurement or censoring.)

In sensitivity analyses of the primary endpoint evaluated with the Single-Stage TMLE, we will adaptively select from the following prespecified set the combination of baseline variables that maximizes empirical efficiency: age, sex, viral suppression status, or nothing (unadjusted). In sensitivity analyses of secondary endpoints adjusting for potentially differential measurement of viral loads, we will include these variables as well as the post-baseline variable of outmigration in the adjustment set in a longitudinal TMLE [13, 14]. Throughout statistical inference will account for clustering through influence curve-based estimation, described above.

As an additional sensitivity analysis, we may define viral suppression as HIV RNA<50 cps/mL.

Finally, given existing programs to support adherence and retention among adolescents and young adults with HIV in study clinics, we may conduct sensitivity analyses to exclude these clinics. We

note both intervention and control participants had full access to these programs; the intervention was added to, not in place of, the standard-of-care.

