3.1 Other potential mediators

Other potential effect mediators include

- switches to second-line therapy
- engagement in care, defined as having any clinic contact in the 6 months preceding the endpoint window
- postpartum status, defined as in two ways: (i) reporting a birth within 6 months of the endpoint viral load measurement, and (ii) reporting a birth within 12 months of the endpoint viral load measurement

To understand the impact of these post-baseline events on viral suppression and other secondary endpoints (described below), we may conduct analogous analyses as for the switch to DTG.

4 Secondary health endpoints

We will evaluate the SEARCH-Youth intervention effect on the following secondary endpoints. For each secondary endpoint (unless noted), a Single-Stage TMLE will be used to evaluate the intervention effect. We will use the same approach to define the primary and secondary analytic populations as for the primary endpoint (viral suppression at 2 years). We will also use the same approach to covariate adjustment, consider the same subgroups, and may implement analogous predictor analyses.

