4.3 Care engagement

We will conduct the following analyses, aiming to capture the multiple ways in which care engagement impacts participants outcomes. Overall and by study arm, we will report the number and proportion of participants who are

- **Engaged at two years:** having any contact with the clinic in the 6 months preceding the start of their endpoint window
- **Retained throughout follow-up:** having contact with the clinic at least once every 120 days since enrollment

where “clinic” refers to the original clinic where the participant enrolled in the study.

For each of these endpoints, we will use the single-stage approach, described above, to obtain point estimates and statistical inference. We test the corresponding null hypotheses with a one-sided test at the 5% significance level. In sensitivity analyses for engagement at two years, we will consider transfers as a success and censor at death. We will also provide clinic-specific estimates of care engagement and retention.

Pending data availability, we may also use the Kaplan-Meier method to estimate the longitudinal probabilities of **lapse**, defined as the first instance of a gap in contact for >120 days, with censoring at death, outmigration, transfer, and the start of the endpoint window. Using the two-stage approach, we will estimate the intervention effect on the probability of lapse by 6, 12, 18, and 24 months and formally test the null hypothesis.

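### The SAP's adjustment for missing viral loads omits care engagement before the endpoint window, so residual bias of unknown size is plausible in those sensitivity and secondary analyses

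*SAP*

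**What the plan says.** SAP section 2 (clinic-level endpoint) first sets the primary analysis apart: "In the primary analysis, the endpoint (viral suppression or failure) is not subject to missingness". Participants without a viral load in the window are scored as failures. TMLE within each clinic is reserved for analyses with missingness or censoring, including sensitivity analysis (ii). For those, the baseline part is fixed as follows: "Our adjustment set will consist of age, sex, and baseline viral suppression status". A single follow-up variable is then added: "Our adjustment set will also include a post-baseline indicator of outmigration".

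SAP 2.1 carries the same set into the pooled approach. Where sensitivity analyses of secondary endpoints allow for unequal ascertainment of the outcome between groups, the plan reads: "we will include these variables as well as the post-baseline variable of outmigration in the adjustment set in a longitudinal TMLE".

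The inclusion paragraph of SAP section 2 removes outmigrants and formal transfers from the primary analysis. One reason given is that "viral loads obtained on participants who outmigrated are likely to be enriched for persons engaged in care".

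Pre-window engagement is defined elsewhere. SAP 3.1 lists as a potential mediator "engagement in care, defined as having any clinic contact in the 6 months preceding the endpoint window". SAP 4.3 makes it a secondary endpoint, "having any contact with the clinic in the 6 months preceding the start of their endpoint window", and counts contact only with the clinic of enrolment.

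**The concern.** Sensitivity analysis (ii) tests whether the result depends on scoring a missing viral load as failure. It is informative only if, given the adjustment set, people with and without a viral load have similar suppression. In the primary population the outmigration indicator takes one value. The adjustment then rests on three baseline variables and uses nothing from two years of follow-up.

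Two links make engagement a natural candidate for what is left out.

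- **Engagement and measurement.** One SAP reason for a missing viral load is that tracking fails and no routine result exists. Someone attending clinic can be measured by routine test or by tracking; someone out of care has only tracking. In the intervention arm, Protocol 8.1.2 tests viral load every 6 months, and the endpoint window can span 90 + 180 = 270 days.
- **Engagement, suppression and arm.** By listing engagement as a potential mediator, SAP 3.1 allows that the intervention may change it and that it may affect suppression.

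If both links hold, people in and out of care are wrongly treated as exchangeable. Suppression is then overstated, and by more in the arm with lower engagement if the other rates are equal. The adjusted risk ratio could give a misleading account of how robust the primary result is.

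**Working it through.** The documents give no rates of engagement, of measurement by engagement, or of suppression by engagement, so there is no plan figure to reproduce. All inputs below are assumptions, used to show a range.

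**Formulas**, within a stratum of the variables already adjusted for. Let e be the proportion engaged, m1 and m0 the probability of a measured viral load if engaged or not, and s1 and s0 the probability of suppression if engaged or not.

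- True proportion: T = e·s1 + (1−e)·s0
- Estimate when engagement is omitted: O = [e·m1·s1 + (1−e)·m0·s0] / [e·m1 + (1−e)·m0]

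O equals T if m1 = m0 or if s1 = s0. Otherwise the error in an arm is the share missing times the gap in suppression between measured and missing people. At 8% missing, a 20-point gap gives 0.08 × 20 = 1.6 points and a 50-point gap gives 4.0 points.

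**One case in full**: m1 = 0.97, m0 = 0.60, s1 = 0.88, s0 = 0.45; engaged 90% intervention, 70% control.

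- Intervention: T = 0.792 + 0.045 = 0.837; O = (0.76824 + 0.027)/0.933 = 0.852
- Control: T = 0.616 + 0.135 = 0.751; O = (0.59752 + 0.081)/0.859 = 0.790
- Risk ratio: true 0.837/0.751 = 1.115; estimated 0.8523/0.7899 = 1.079. Control missing: 1 − 0.859 = 14.1%.

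**Range**, with m1 = 0.97 and s1 = 0.88 throughout:

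| Engaged, intervention / control | m0 | s0 | Control missing | True RR | Estimated RR | Shift |
|---|---|---|---|---|---|---|
| 90% / 70% | 0.50 | 0.35 | 17.1% | 1.147 | 1.086 | −0.061 |
| 95% / 80% | 0.50 | 0.30 | 12.4% | 1.114 | 1.063 | −0.051 |
| 90% / 70% | 0.60 | 0.45 | 14.1% | 1.115 | 1.079 | −0.035 |
| 95% / 85% | 0.64 | 0.45 | 8.0% | 1.053 | 1.036 | −0.016 |
| 90% / 70% | 0.75 | 0.55 | 9.6% | 1.085 | 1.070 | −0.014 |
| 90% / 85% | 0.60 | 0.45 | 8.6% | 1.026 | 1.018 | −0.009 |
| 90% / 80% | 0.85 | 0.60 | 5.4% | 1.034 | 1.031 | −0.003 |
| 90% / 90% | 0.50 | 0.30 | 7.7% | 1.000 | 1.000 | 0 |

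In the last row each arm is overstated by 2.7 points, but equally, so the risk ratio does not move.

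**If tracking of people out of care differs by arm.** Take no true effect, 80% engaged in both arms, m1, s1 and s0 as in the full case, and m0 = 0.80 in the intervention arm against 0.50 in control.

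- Intervention: O = (0.68288 + 0.072)/0.936 = 0.8065
- Control: O = (0.68288 + 0.045)/0.876 = 0.8309
- Risk ratio: 0.971 instead of 1.000. With the arms swapped it is 1.030. With 90% engaged and the first ordering it is 0.985.

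The direction is therefore not guaranteed once measurement differs by arm. No section of either document indicates such a difference in tracking.

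**Data per clinic.** At 8% missing and 50 participants, about 0.08 × 50 = 4 people per clinic lack a viral load.

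**The case against.** A reader might infer that the SAP itself concedes that measured viral loads in general over-represent people in care. It does not. The remark concerns outmigrants only, as a further reason to exclude them from the primary analysis. For other participants the listed reasons for a missing value are declining, not being found with no routine result, and a sample taken after database closure. The SAP also promises tracking, including home visits, irrespective of care status. This limits the argument, but it does not close it: the promise covers attempts, not success, and a routine result is more likely for someone who attends.

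A reader might also infer that the adjusted analyses are biased, or that the main result is. The first is not shown, because bias needs both dependencies to persist given age, sex and baseline suppression. The second does not follow from the SAP, which scores missing as failure. Protocol 9.4.2 does place a TMLE adjustment for incomplete viral loads in the primary analysis. That difference needs reconciling, but this point concerns the SAP's analyses.

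Three further objections carry weight.

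- **The larger shifts rest on strong inputs.** They use engagement gaps of 15 to 20 points, and all but one of those cases have control missingness of 12% to 17%. Protocol 9.4.3.1 expects 2-year loss to follow-up below 8%, although that is not the same as a missing viral load.
- **There are other checks.** The SAP plans a complete-case analysis and arm-specific counts of suppressed, unsuppressed, dead and missing, from which other assumptions can be bounded.
- **The added covariate has limits.** With about 4 missing per clinic, clinic-level models may fail. SAP 2.1 prefers the two-stage approach when measurement is differential, so moving to the pooled version is a compromise. The SAP 4.3 indicator also codes someone in care at a new clinic as not engaged.

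These bear on the size of the point and the form of the fix. They do not explain why the adjustment in the primary population should use no follow-up information when a suitable variable is already defined.

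**Conclusion.** The concern holds for the sensitivity and secondary analyses that adjust for missing viral loads: residual bias is plausible, and its size is unknown. It is zero if either measurement or suppression is independent of engagement given the adjustment set. With mild dependence the risk ratio moves by a few thousandths. With marked dependence on both it moves by about 0.01 to 0.06, toward 1 when only engagement differs between arms. At about 8% control missingness and a 10-point engagement gap, 1.053 becomes 1.036. Every one of these figures rests on assumed rates. In those cases the omission would understate a benefit rather than create one; only arm-differential tracking, which the documents do not suggest, could push either way. The SAP's primary estimate and the sample size are not affected.

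**What to change.** Add the SAP 3.1/4.3 indicator of clinic contact in the 6 months before the endpoint window to the missingness adjustment set in SAP 2 and 2.1.

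- **Pooled analysis.** Enter it as a post-baseline, time-varying covariate in the longitudinal TMLE of SAP 2.1, as already planned for outmigration. It should not be treated as a baseline covariate, because the intervention may change it.
- **Clinic-specific stage 1.** Include it where cell counts allow, under a minimum-count rule stated in advance. Each clinic is in one arm, so using it there to model measurement does not block the intervention effect. Where counts are too small, report the pooled Single-Stage version.
- **Population with transfers and outmigrants.** Pair it with a transfer indicator, or count documented contact at any clinic, because the SAP 4.3 definition sees only the original clinic.

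If engagement is left out, the SAP should say why viral loads can be taken as missing at random given the current set.

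The main variable is already defined for other analyses. The statistical cost is sparser cells and somewhat wider intervals in small clinics. Counting contact at other clinics may need extra record review.
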